15.1.1 All Adverse Events

All AEs recorded during the course of the trial (ie, assessed from signature of informed consent until the end of the Follow-up/End of Trial visit) will be coded according to MedDRA latest version and assigned to a SOC and PT.

TEAEs will be summarized by severity, using MedDRA latest version preferred term as event category and MedDRA primary system organ class (SOC) body term as Body System category. The severity of AEs will be graded using the “National Cancer Institute - Common Terminology Criteria for Adverse Events” (NCI-CTCAE) guideline, version 5.0 (publication date: 27 Nov 2017), as detailed in the study protocol.

TEAEs related to trial treatment are those events with relationship missing, unknown or related.

The following will be summarized in an overview table with the number and percentage of subjects (and the number of events) by treatment and overall:

- Any TEAEs
- Any trial treatment related TEAEs
- Any serious TEAEs
- Any trial treatment related serious TEAEs
- Any TEAE (grade ≥ 3)
- Any trial treatment related TEAEs (grade ≥ 3)
- Any TEAEs leading to death
- Any trial treatment related TEAEs leading to death

TEAEs will be summarized by treatment and overall in tables with:

- The number and percentage of subjects by treatment with at least one TEAE and the number of events overall and by SOC and PT. Group/SOC terms will be sorted alphabetically and PTs within each group/SOC term will be sorted by descending frequency.
- The number and percentage of subjects by treatment with at least one non-serious TEAE and the number of non-serious TEAE applying frequency threshold of 5%. Group/SOC terms will be sorted alphabetically and PTs within each group/SOC term will be sorted by descending frequency.

In addition the following tables will be provided. Group/SOC terms will be sorted alphabetically and PTs within each group/SOC term will be sorted by descending frequency (based on all treatment groups combined):

- A table by severity of TEAEs with the number and percentage of subjects by treatment with at least one TEAE and the number of events by SOC and PT.
- A table by relationship to trial treatment with the number and percentage of subjects by treatment with at least one TEAE and the number of events by SOC and PT.

Pre-treatment AEs (AEs with onset after informed consent but before start of treatment) and TEAEs will be listed separately.

15.1.2 Adverse Events Leading to Treatment Discontinuation

TEAEs leading to permanent discontinuation of trial treatment will be summarized by treatment and overall including number of subjects, percentage and number of events.

A listing of TEAEs leading to permanent discontinuation of a trial treatment will additionally be provided.

15.2 Deaths, Other Serious Adverse Events, and Other Significant Adverse Events

15.2.1 Deaths

All deaths as well as reason for death will be based on information from the “Report of Subject Death” CRFs.

Listing of deaths, if any, will be provided displaying date and cause of death (including TEAE leading to death and relatedness to trial treatment, when applicable), and date and time of treatment administration.

15.2.2 Serious Adverse Events

A summary table of SAEs, if any, by treatment and overall will be provided displaying the number and percentage of subjects by treatment with at least one SAE and the number of SAE overall and by system organ class and preferred term. Group/SOC terms and PTs within each group/SOC term will be sorted alphabetically.

Listing of SAEs, if any, will be provided in addition.

15.2.3 Other Significant Adverse Event

15.2.3.1 Adverse Events of Special Interest

Healthy subjects might experience asymptomatic elevations in serum lipase and amylase. Any elevation in serum lipase and amylase of Grade ≥ 3 will lead to the recording of an AE of special interest (AESI). The severity of these AEs should be defined based on clinical judgment of the Investigator and defined according to NCI-CTCAE Severity Scale.

Adverse events of special interest will be presented in a separate data listing.

15.3 Clinical Laboratory Evaluation

All laboratory data will be reported with SI units. Laboratory parameters will be listed by subject and time-point and summarized indicating the treatment at the respective time-point using descriptive statistics for absolute values and change from baseline over time and by post-dose CTCAE grade shift relative to baseline. Shift tables will be based on NCI-CTCAE grades, where possible, and on normal ranges otherwise.

Shift tables will be presented for:

- End of Trial versus Screening
- Discharge Day 4 versus Pre-dose (Tepotinib administration) within periods.

Laboratory values that are outside the normal range will also be flagged in the data listings, along with corresponding normal ranges and NCI-CTCAE grade. Any out-of-range values will additionally be listed separately including NCI-CTCAE grade.

See section 7.4.3 of the clinical study protocol for a table of the safety laboratory evaluations.

Safety laboratory values are separated into:

- Hematology
- Biochemistry

- Urinalysis
- Other tests

Tables will be produced for the groups Hematology, and Biochemistry.

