Further, justification based on the accumulated safety experience is provided. During the development of tepotinib, in all 3 studies performed in healthy subjects (n = 79), the subjects well tolerated a single or 3 doses of tepotinib (different dose levels up to 500 mg single dose). All treatment-emergent adverse events (TEAEs) were mild to moderate, except 1 Grade 3 asymptomatic lipase elevation in 1 subject. TEAEs did not show a pattern across all 3 trials. No serious adverse events (SAEs) were reported and no subject died. No clinically significant findings regarding laboratory parameters, vital signs and electrocardiogram (ECG) including corrected QT interval according to Fridericia (QTcF) values were noted.

Elevations in serum lipase and amylase are considered as the only identified risks for subjects administered tepotinib so far. These elevations were observed in 5 of 79 healthy subjects exposed to tepotinib and were mild to moderate in severity (exception: 1 Grade 3 lipase elevation), transient

and without apparent dose dependency. All increases of serum amylase/lipase were asymptomatic and not associated with pancreatitis.

Subjects enrolled in this study might be exposed to a potential risk, including pancreatic enzyme elevation. However, inclusion of healthy subjects is justified when the administration of tepotinib is limited to a single dose or short term multiple administrations that will be given under close monitoring conditions to reduce the risk for untoward effects.

Since loss of c-Met induces teratogenic effects in c-Met knockout mice, and since a pilot embryofetal development study in rabbits revealed maternotoxic effects and a dose-dependent increased number of skeletal malformations (teratogenicity), stringent criteria are applied to ensure exclusion of women of childbearing potential in this study. Only healthy women that are known to be postmenopausal or surgically sterile (ie due to hysterectomy, bilateral oophorectomy, or bilateral salpingectomy) will be enrolled in this study (for details see Section 5.3.1). Male subjects will be required to take precautions with regards to female partners.

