7.1.2 Treatment Periods

The subjects willing to participate in the trial will only be included when all Screening examination procedures have demonstrated that all inclusion criteria and none of the exclusion criteria apply. Subjects will be assigned to a random number within the trial prior to the first administration.

For time points and assessments please refer to [Table 1](#) (Parts A, B and C).

Day -1 (Admission)

Subjects will be admitted to the clinic in the morning of Day -1 until completion of the 72 h assessments in the morning of Day 4 of each period.

In each period, the following assessments will be performed:

- Physical examination
- Measurement of vital signs
- 12-lead safety ECG recording
- Blood and urine sampling for safety laboratory assessments
- Pregnancy test (in urine)
- Urine drug screen (including test for cotinine)
- Alcohol breath test
- Assessment of AEs
- Documentation of concomitant medication
- Evaluation of inclusion and exclusion criteria (Period 1 only)

- Blood sampling for PGx (Period 1 only).

Days 1 to 4 (inpatient)

Prior to dosing on Day 1 the following assessments will be done:

- Measurement of vital signs
- 12-lead safety ECG recording
- Blood and urine sampling for safety laboratory assessments
- Pre-dose PK blood sample for determination of tepotinib and its metabolites.

After completion of pre-dose assessments study drug will be administered in the morning of Day 1 of each period as the following:

Part A: Study drug will be administered in both periods in the fasted state together with 240 mL of water.

Parts B and C: Study drug will be administered in one period in a fasted state and in the other period 30 min after start of a standardized high fat, high calorie breakfast, which must be consumed completely within 25 min. The study drug will be administered together with 240 mL of water.

A detailed guidance on dosage and administration is provided in Section [6.2](#).

After dosing the following assessments will be performed at the time points given in the Schedule of Assessments ([Table 1](#)):

- PK blood samples for determination of tepotinib and its metabolites will be taken regularly until 72 h (Day 4) post-dose before discharge (for time points please refer to Table 1)
- Measurement of vital signs and 12-lead safety ECG recordings on Day 1 (2 h and 8 h post-dose), Day 2 and Day 4 before discharge
- Blood and urine sampling for safety laboratory assessments on Day 2 and Day 4 before discharge

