Investigators must also systematically assess the causal relationship of AEs to the IMP (including any other non-IMPs, or medical procedures, as applicable, etc.) using the following definitions. Decisive factors for the assessment of causal relationship of an AE to the IMP include, but may not be limited to, temporal relationship between the AE and the IMP, known side effects of the IMP, medical history, concomitant medication, course of the underlying disease, trial procedures.

Unrelated: Not reasonably related to the IMP. AE could not medically (pharmacologically/clinically) be attributed to the IMP/study treatment under trial in this clinical trial protocol. A reasonable alternative explanation must be available

Related: Reasonably related to the IMP. AE could medically (pharmacologically/clinically) be attributed to the IMP/study treatment under trial in this clinical trial protocol.

Abnormal Laboratory Findings and Other Abnormal Investigational Findings

Abnormal laboratory findings and other abnormal investigational findings (for example, on an ECG trace) should not be reported as AEs unless they are associated with clinical signs and symptoms, lead to treatment discontinuation or are considered otherwise medically important by the Investigator. If a laboratory abnormality fulfills these criteria, the identified medical condition (for example, anemia, increased ALT) must be reported as the AE rather than the abnormal value itself.

Serious Adverse Events

An SAE is any untoward medical occurrence that at any dose:

- Results in death
- Is life-threatening (Note: The term “life-threatening” refers to an event in which the subject is at risk of death at the time of the event, not an event that hypothetically might have caused death if it was more severe.)
- Requires inpatient hospitalization or prolongs an existing hospitalization
- Results in persistent or significant disability or incapacity
- Is a congenital anomaly or birth defect

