8.6.4 Analysis of Safety and Exploratory Endpoints

Safety data analysis will be conducted on the Safety Analysis Set of each part. The number and percentage of subjects experiencing at least 1 TEAE will be summarized by treatment as will the number of events. Tables by relationship to study drug and by severity will be generated. AEs will be coded using Medical Dictionary for Regulatory Activities terminology. All laboratory data will be reported with SI units.

Laboratory parameters will be summarized using descriptive statistics for absolute values and change from baseline over time, by post-dose shifts relative to baseline, and data listings of clinically significant abnormalities/out of the normal range.

Vital signs and ECG data will be summarized by changes from baseline values by treatment using descriptive statistics. Clinically significant ECG findings for individual subjects will be listed and summarized as appropriate.

PK concentrations will be descriptively summarized. Individual and mean concentration-timeplots will be produced in linear and log-linear scale.

Exploratory endpoints will be analyzed with descriptive statistics.

8.7

Interim and Additional Planned Analyses

A two-stage design is used in Part A. Based on the measured variability, the corresponding power for the number of subjects in Stage 1 will be estimated. If the power is < 80%, an interim analysis will be performed. The significance level for both the interim analysis and the final analysis will then be set to 0.0294. For details refer to section 8.6.2.

9

Ethical and Regulatory Aspects

9.1

Responsibilities of the Investigator

The Investigator is responsible for the conduct of the trial at the site and will ensure that the trial is performed in accordance with this protocol, the ethical principles outlined in the Declaration of Helsinki, ICH GCP [7], and any other applicable regulations. The Investigator must ensure that only subjects who have given informed consent are included in the trial.

9.2

Subject Information and Informed Consent

An unconditional prerequisite for each subject prior to participation in the trial is written informed consent, which must be given before any trial-related activities are carried out. Adequate information must therefore be given to the subject by the Investigator or an appropriate designee (if local regulations permit) before informed consent is obtained.

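### The only within-period laboratory shift table is Day 4 versus pre-dose, so a Grade 1-2 lipase or amylase rise confined to Day 2 and not reported as an AE is counted by grade and treatment in no table

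*SAP*

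**What the plan says.** **Schedule.** Protocol 7.1.2 and Table 1 place safety laboratory tests at pre-dose and then at two post-dose times in each period: "Blood and urine sampling for safety laboratory assessments on Day 2 and Day 4 before discharge". Lipase and amylase are in the biochemistry panel (Protocol Table 2).

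**Planned laboratory summaries.** Protocol 8.6.4 says that laboratory parameters will be summarized, among other ways, "by post-dose shifts relative to baseline, and data listings of clinically significant abnormalities/out of the normal range". SAP 15.3 opens in similarly general terms. Parameters are to be "summarized indicating the treatment at the respective time-point using descriptive statistics for absolute values and change from baseline over time" and also "by post-dose CTCAE grade shift relative to baseline". It then names two shift tables. One compares End of Trial with Screening. The other is "Discharge Day 4 versus Pre-dose (Tepotinib administration) within periods". No Day 2 shift and no worst-post-dose shift is named. SAP section 7 declares no change from the protocol's methods.

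**Known signal.** Protocol section 3 states: "Elevations in serum lipase and amylase are considered as the only identified risks for subjects administered tepotinib so far". It reports them in 5 of 79 healthy subjects, mild to moderate apart from one Grade 3 lipase elevation, transient, asymptomatic and without apparent dose dependency.

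**Adverse event rules.** Under Protocol 7.4.1.1, abnormal laboratory findings "should not be reported as AEs unless they are associated with clinical signs and symptoms". The same sentence also excepts findings that lead to discontinuation or that the investigator considers medically important. Protocol 7.4.3 adds that abnormalities judged clinically relevant are reported as AEs. Lipase or amylase elevations of Grade 3 or higher are recorded as AEs of special interest (Protocol 7.4.1.4, SAP 15.2.3.1).

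**The concern.** A shift table at one fixed late time suits an abnormality that persists. It suits a transient one less well: a subject who rises and recovers before that time is shown as having no shift. Here the one laboratory signal already attributed to the drug is described as transient, and the plan takes an intermediate sample that the shift table does not use.

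The AE tables do not necessarily fill the gap. The earlier elevations were asymptomatic and, with one exception, below the grade at which recording is compulsory. Below that grade, recording depends on the investigator's judgement.

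At stake is how completely a secondary objective is reported, namely the safety and tolerability of TF3 and TF2 fasted and fed, for which changes in safety laboratory assessments are a named endpoint. No hypothesis test, sample size or PK result depends on it.

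**Working it through.** The plan gives no figure to reproduce, so the check is mainly a comparison of text, followed by a rough scale.

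**Step 1. Follow one hypothetical subject through the planned outputs.** Suppose lipase is Grade 0 at period pre-dose, Grade 2 on Day 2 and Grade 0 on Day 4, without symptoms, and the investigator does not judge it clinically relevant.

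| Planned output | Source | Is the Day 2 rise visible? |
|---|---|---|
| Shift, Day 4 versus pre-dose | SAP 15.3 | No; shown as Grade 0 to Grade 0 |
| Shift, End of Trial versus Screening | SAP 15.3 | No; does not use Day 2 |
| Descriptive statistics over time, with treatment | SAP 15.3, SAP 9 | Yes, as part of the Day 2 distribution (Q3, maximum); no count by grade |
| TEAE tables by treatment and severity | SAP 15.1.1 | No, because not reported as an AE |
| AESI listing | SAP 15.2.3.1 | No, because below Grade 3 |
| By-subject listing and separate out-of-range listing with grade | SAP 15.3 | Yes, individually |

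The rise is visible in two kinds of output. Neither gives the number of subjects by CTCAE grade and treatment.

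**Step 2. Vary the example to find the limits of the gap.**
- Grade 3 or higher on Day 2: recorded as an AESI. If treatment-emergent, it also counts in the by-treatment TEAE tables, including the overview row for Grade 3 or higher.
- Grade 1-2 but judged clinically relevant or medically important: reported as an AE and counted by treatment and severity.
- Grade 1-2 and unchanged on Day 4: counted in the existing shift table.

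The gap is therefore the intersection of three conditions: Grade 1-2, back to baseline grade by Day 4, and not reported as an AE.

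**Step 3. Compare with the ECG rule in the same SAP.** SAP 15.5 counts subjects by QTcF category at any post-dose assessment, by treatment. Protocol section 3 reports no clinically significant ECG or QTcF findings in healthy subjects. The laboratory parameters with an identified signal thus receive a narrower categorical summary than one without.

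**Step 4. Scale.**
- Input: 5 of 79 (Protocol section 3). Rate = 5/79 = 6.3%; exact (Clopper-Pearson) 95% CI 2.1% to 14.2%.
- If that rate applies per subject to the planned 40 + 12 + 12 = 64 subjects: 64 × 5/79 = 4.1 with any elevation. Over the interval, 64 × 0.0209 = 1.3 to 64 × 0.1416 = 9.1.
- If it is instead assumed to apply to each dose: 40 × 5/79 = 2.5 per treatment in Part A (0.8 to 5.7), and 12 × 5/79 = 0.8 per treatment in Part B or Part C (0.25 to 1.7). The chance of at least one is 1 − (74/79)^40 = 93% and 1 − (74/79)^12 = 54% respectively.

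These are counts of elevations of any grade and timing. They are ceilings under the stated rates, not estimates of what is missed. The fraction satisfying all three conditions in Step 2 is not given and cannot be derived, so it may be anything from zero upward.

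**The case against.** The strongest reply is that little is hidden. Day 2 biochemistry is in the descriptive tables with treatment indicated. Those tables carry quartiles and extremes, so one marked rise would show as a maximum. Severe or clinically relevant rises reach the TEAE tables. Every out-of-range value is listed with its grade, and with parts of 40, 12 and 12 subjects a medical reader can go through the listing case by case. All of this stands, and it rules out the broader inference that Day 2 elevations are not tabulated by treatment at all. What remains is that a maximum shows that someone rose, not how many subjects did or to what grade, and that a listing leaves the counting to the reader.

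A reader might also infer that Day 2 matters because it lies closest to peak exposure. The documents do not support this. The reported median tmax of 8 h (range 4 to 24 h, Protocol 5.2.4) is from a 500 mg TF2 study that Protocol Table 5 marks as fed, whereas Part A is fasted. The elevations showed no apparent dose dependency, and nothing links their timing to concentration. Nor does transient mean resolved by Day 4.

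Finally, one might call the Day 4 restriction an undeclared departure from the protocol. That is too strong. Protocol 8.6.4 plans summaries "by post-dose shifts relative to baseline" without naming a time, Protocol 8.6.1 leaves details to the SAP, and Day 4 versus pre-dose is a post-dose shift. The general wording in both documents is broader than the table named, which favours adding a table but does not establish a contradiction.

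**Conclusion.** The point holds in a narrow form. Under SAP 15.3 as written, a Grade 1-2 lipase or amylase change seen only on Day 2 and not reported as an AE is shown as no shift, and no other table counts it by grade and treatment. It remains visible in listings and continuous summaries.

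The size is unknown and may be zero. The scale of about 4 subjects with any elevation assumes that the earlier rate, pooled over several dose levels and formulations, carries over to this trial, and that Part A stops at 40 subjects. The missed number further depends on onset and duration, which the documents do not give.

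Severity is minor. This is a descriptive secondary safety summary, and the bioequivalence and food-effect analyses are untouched.

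**What to change.** In SAP 15.3, add a within-period shift table of the worst post-dose CTCAE grade (the higher of Day 2 and Day 4) versus period pre-dose, by treatment and separately for Parts A, B and C. It should cover at least lipase and amylase. Keep the Day 4 versus pre-dose table beside it, since that one shows what persisted at discharge. This follows the any-post-dose rule already used for QTcF in SAP 15.5 and fits the general post-dose wording of Protocol 8.6.4.

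Inclusion criterion 7 asks that lipase and amylase not exceed the upper limit of normal at Screening. Most baseline grades should therefore be 0, and the table should be short and easy to read.

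The cost is one additional table, to be specified before database lock. It needs no new samples or visits and no change to the protocol's assessments.

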15.4 Vital Signs

Vital signs will be listed by subject and time-point and summarized for absolute values and changes-from-baseline (period-baseline) by visit and treatment using descriptive statistics. Descriptive statistics tables will start at baseline.

15.5 ECG Evaluation

ECG data will be listed by subject and time-point and summarized by absolute values and changes-from-baseline (period-baseline) by treatment group using descriptive statistics. Baseline is the pre-dose assessment in each period. See section 9 for a description of how missing baseline values are handled. Descriptive statistics tables will start at baseline. Clinically significant ECG findings for individual subjects will be listed and summarized.

The time intervals [PR, QRS, RR, QT and corrected QT intervals [based on Fridericia's formula, QTcF] will be summarized descriptively by treatment.

The Fridericia's Correction (QTcF) is derived as follows:

$$\text{Fridericia's Correction (QTcF)} \quad QTc_f = \frac{QT}{\sqrt[3]{RR}}$$

where: RR = RR-interval measured in seconds.

Observed QTcF values will be categorized according to their absolute values into the categories

- ≤ 430 ms,
- > 430 and ≤ 450 ms,
- > 450 and ≤ 480 ms,
- > 480 and ≤ 500 ms, and
- > 500 ms,

and categorized according to their absolute change from period baseline into the categories

- ≤ 30 ms,
- > 30 and ≤ 60 ms, and
- > 60 ms.

The number and percentage of subjects by these categories at any post-dose assessment will be tabulated by treatment group. All ECG measurements and changes from period baseline will be listed, with abnormalities (as reported of the investigator on the ECG eCRF page) indicated.

Investigator reported interpretation results will also be tabulated by treatment using the number and percentage of subjects for each interpretation category (Normal, Abnormal Not Clinically Significant [NCS], Abnormal Clinically Significant [CS]).

16 Analyses of Other Endpoints

